10.1.3 Serious Adverse Events (SAEs)

The Principal Investigator shall document all SAEs in a subject receiving study drug until completion of the study and must be reported to the Repos Therapeutics Inc. Safety Monitor within 24 hours by Fax or telephone, even if the SAE does not appear to be drug-related. This report should include all available information at the time of notification. This notification should be followed with submitting a SAE Report Form provided by Repos Therapeutics Inc, and notifying the IRB.

All additional follow-up reports must be reported to the Repos Therapeutic Inc. monitor as soon as available.

[figure not shown]
Cases of liver transaminases that increase above 3 times the upper limit of normal must be reported as SAEs regardless of whether the above defined SAE criteria are met.

11. CONCOMITANT MEDICATIONS

11.1 Prohibited Medications

The following medications are prohibited during the study and during the 6-month follow up after discontinuation of study medication:

- Testosterone
- Progestin
- Androgen
- Estrogen
- Anabolic steroids
- DHEA
- Other hormonal products
- Any other treatment for uterine fibroids

[figure not shown]
11.2 Other Medications Taken During the Study

Any other prescription or over-the-counter medication taken during the study will be recorded in the appropriate section of the CRF. Subject must be on a stable dosage of approved concomitant medications at least 48 hours prior to drug administration.

12. STATISTICAL METHODS

12.1 Determination of Sample Size

Up to 50 female subjects, 15 per dose arm, meeting the inclusion/exclusion criteria will be randomized in a 1-1-1 fashion with the expectation that approximately 45 will be fully eligible for efficacy analyses. The primary endpoint is amenorrhea.

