Study Design and Duration of Treatment:	
This study is a phase 2 3-arm-study with two 18-week dosing courses. The study will be conducted in two stages.
 
In the first stage, women will undergo a baseline assessment period with no treatment, until 15-20 days after the start of their second complete menstrual event. During this phase a pictorial blood loss assessment chart will be utilized as well as sanitary products collected from their first menstrual event, for alkaline hematin assay, to determine menstrual blood loss and confirm eligibility.
 
In the second stage, subjects will be randomized into one of 3 arms in a 1-1-1 fashion and receive two 18-week courses of treatment at their randomized dose (6 mg, 12 mg or placebo), separated by an off-drug interval (ODI). The start of the first 18-week course of treatment (Course 1) should commence 15-20 days after the start of their previous menses. Subjects should be instructed to continue vaginal dosing during their menses throughout the study and not to have sex or insert anything in the vagina for at least 1 hour after the capsule is inserted. Once dosing for Course 1 is stopped, subjects will be followed until menses return. The start of the second 18 week course of treatment (Course 2) will commence 15-20 days after the start of their menses following withdrawal of drug after Course 1 has been completed. During the ODI, subjects will continue to record study information in the daily paper diary and PBAC charts as well as collect sanitary products for alkaline hematin assay.
 
After completion of stage 2 dosing (Courses 1 and 2), subjects will be followed through the subsequent 6 menses (recovery menses plus an additional 5 menstrual events), the subject may be offered the opportunity to enroll in an open-label extension study. Subjects who fail to achieve amenorrhea may enroll in the extension study at Visit 19. Amenorrhea is defined as any 28-day period during treatment (not including the ODIs) without a bleeding score >1. Throughout the study women will record study information in the diary, PBAC, and questionnaires as outlined in the study procedures.
 
Subjects will collect and return used sanitary materials for alkaline hematin assay for their first menstrual event during screening, for the recovery menses menses following Course 1, for the 28 days leading

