	up to the end of treatment in Course 2, and for the 1 st , 2 nd , 4 th and 6 th menstrual cycles after end of treatment in Course 2.
Subject Population:	The study will enroll healthy adult, pre-menopausal women with confirmed uterine fibroids via MRI and confirmed menorrhagia (>120 mL blood loss per menstrual cycle by historical PBAC assessment, nominal 28 days to ensure a MBL of at least 80 mL by Alkaline Hematin Assay). Subjects with evidence of prior heavy blood loss may be enrolled at the sponsor's discretion.
Number of Subjects:	Up to 45 female subjects, 15 per dose arm
Number of Sites	Approximately 10 sites
Study Duration:	Total participation in the study is approximately 18 months.
Study Endpoints	
The primary endpoint will be:
 
• Percentage of subjects who become amenorrheic after one course of treatment 
Secondary endpoints will be:
 
• Percentage of subjects who become amenorrheic after 2 courses of treatment

	
• Change and percentage change in PBAC score over the course of the study. Specifically comparing the baseline menstrual cycle to the matching end-of-study period leading up to Week 18 and the end of treatment as well as comparing the baseline PBAC to the ODI time periods.• Percentage change in UFSQOL Symptom Severity score (UFS-SSS) comparing Week 18 to Baseline (three month look back) and for the ODI.• Percentage change in the individual UFS-SSS sub scores• Percentage change from baseline in total uterine fibroid volume measured by MRI                   
Statistical Methods:	A Statistical Analysis Plan (SAP) will be developed prior to unblinding of the data that will outline all planned analyses and analysis populations. The first efficacy analysis will be conducted when all subjects complete the first cycle of treatment. A second analysis will summarize the subject's additional treatment cycles which will be conducted after all subjects complete study treatment

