12.2.2 Efficacy Analyses

A Statistical Analysis Plan (SAP) will be prepared prior to unblinding of the study data. Efficacy analyses will be conducted in the Intent-to-Treat population, which will consist of all subjects who are randomized and who receive study drug.

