12.3 General Statistical Issues

A Statistical Analysis Plan (SAP) will be finalized prior to unblinding the study. For the efficacy variables a last observation forward approach will be used to impute missing data to generate a complete ITT data. If there are no post-baseline efficacy data then a value of no change will be imputed for the missing efficacy measure. Statistical significance will be declared if the two-sided p-value is ≤ 0.05 .

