### **3.2 SAMPLE SIZE CALCULATION/JUSTIFICATION**

Up to 50 female subjects, 15 per dose arm, meeting the inclusion/exclusion criteria will be randomized in a 1-1-1 fashion with the expectation that approximately 45 will be fully eligible for efficacy analyses. The primary endpoint is amenorrhea (no vaginal bleeding intensity > 1). A

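### The planned sample size is stated inconsistently: a ceiling of 45 in the protocol synopsis, but up to 50 randomized in protocol 12.1 and SAP 3.2, each with 15 per arm

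*Protocol*

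**What the plan says.** Three places in the current documents give the planned number.

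- Protocol synopsis, Number of Subjects: "Up to 45 female subjects, 15 per dose arm". The synopsis does not say whether this counts women enrolled, randomized or analysed. It describes the allocation as follows: "subjects will be randomized into one of 3 arms in a 1-1-1 fashion".
- Protocol 12.1: "Up to 50 female subjects, 15 per dose arm, meeting the inclusion/exclusion criteria will be randomized in a 1-1-1 fashion". The sentence then gives an expectation of about 45 for the efficacy analyses.
- SAP 3.2 has the same wording as protocol 12.1, including "with the expectation that approximately 45 will be fully eligible for efficacy analyses". It appears both in the SAP version written to Amendment 4 and in the one written to Amendment 3.

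Protocol 12.2.2 bases efficacy on the "Intent-to-Treat population, which will consist of all subjects who are randomized and who receive study drug". SAP 4.1 defines the same set and SAP 6.8 uses it for efficacy. The only other analysis set visible in the SAP is the Safety population (4.2).

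**The concern.** A sample size is a figure that sites, ethics boards and the statistician all rely on, and here they would read different limits. Someone working from the synopsis would treat women 46 to 50 as enrolled beyond plan. Someone working from section 12.1 or the SAP would not.

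The per-arm figure does not settle the matter, because 15 appears under both totals. In section 12.1 and SAP 3.2 it is attached grammatically to the women randomized, although it matches the number expected for analysis. A reader cannot tell whether 15 per arm is what the randomization list should deliver or what should remain for the efficacy comparison.

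**Working it through.** **Inputs.** Three arms, 1-1-1 (protocol synopsis). Fifteen per arm (synopsis, 12.1, SAP 3.2). Ceiling of 45 (synopsis) or 50 (12.1, SAP 3.2). About 45 eligible for efficacy analyses (12.1, SAP 3.2). No loss rate is stated; the one used below is implied by the documents' own figures.

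**Step 1: reproduce the stated figures.**
- Arms × number per arm: 3 × 15 = 45. This gives the synopsis total and the expected eligible number in 12.1.
- Implied loss from 50 to 45: 1 − 45/50 = 10%.
- Inflating for that loss: 45/(1 − 0.10) = 50. This gives the number randomized in 12.1.
- For comparison, a loss of 5% would need 45/0.95 = 47.4, so 48 randomized. A loss of 15% would need 45/0.85 = 52.9, so 53.

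Section 12.1 is therefore coherent if 15 per arm means eligible women.

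**Step 2: read 15 per arm as women randomized, which is how the sentence is built.**
- 3 × 15 = 45, five short of 50.
- 50/3 = 16.7, so equal allocation of 50 gives 17/17/16.

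**Step 3: take each ceiling in turn.**

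| Ceiling on women randomized | Randomized per arm | Eligible at 10% loss | Eligible per arm |
|---|---|---|---|
| 50 | 16–17 | 50 × 0.90 = 45 | 15 |
| 45 | 15 | 45 × 0.90 = 40.5, about 40 | 13–14 |

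Under a ceiling of 45, an expectation of about 45 eligible requires almost no loss. It cannot be combined with the 10% implied in 12.1.

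**Step 4: size of the effect on precision.** For a difference between two proportions that are both near 50% (an assumption, since no response rates are visible), the 95% half-width is 1.96 × √(2 × 0.25/n).
- n = 15: 1.96 × √(0.5/15) = 0.358, about 36 points.
- n = 16.7: 1.96 × √(0.5/16.7) = 0.339, about 34 points.

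The ratio of the two half-widths is √(45/50) = 0.949 whatever the rates, so the interval narrows by about 5%. Because p(1 − p) is largest at 50%, the gap of about 2 points is the most that this formula can give. With assumed rates of 5% and 50%, for example, 1.96 × √((0.0475 + 0.25)/n) gives 27.6 points at n = 15 and 26.2 at n = 16.7, a gap of about 1.4 points.

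**The case against.** The strongest answer is that section 12.1 explains its own numbers: 50 are randomized so that about 45 are available, and 45 is three times 15. That stands. A reader who stops at the allocation ratio might infer a plain error of multiplication, but the rest of the sentence does not support that. Nor is it a fault that 50 does not divide by three. The figure is a ceiling and 1-1-1 is a ratio, so 17/17/16 is ordinary. What remains is that the synopsis gives 45 without calling it an analysed number, and that 12.1 attaches 15 per arm to the women randomized.

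Three further inferences are tempting, and the documents do not support them.

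- *No efficacy set smaller than the number randomized can exist.* The Intent-to-Treat set requires receipt of study drug, so women randomized but never dosed fall outside it. An expectation of 45 from at most 50 is compatible with that definition, although the documents do not say why about five women would be lost.
- *The eligibility phrase sets up a later filter that drops 10% of women.* The visible plan defines only Intent-to-Treat and Safety sets and runs efficacy on the former. An expectation in a sample-size paragraph does not create an analysis population.
- *A ceiling of 45 leaves no room for dropout.* Dosed women who stop early stay in the efficacy analysis. Protocol 12.3 and SAP 6.1 carry the last observation forward, and 12.3 imputes no change where there are no post-baseline data. Dropout after dosing does not by itself reduce the number analysed.

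The SAP 3.2 text breaks off after the head count. The absence of a visible power calculation is therefore not held against the plan, and the missing text might clarify the per-arm figure. It could not remove the mismatch with the synopsis.

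**Conclusion.** The inconsistency is real but minor. The current text carries two ceilings, 45 and 50, and a per-arm figure that fits only one reading of each. The likeliest intention is 50 randomized for about 45 analysed, but that is an inference from the implied 10% loss, and the synopsis does not say it. No visible test, analysis set or decision rule changes with the answer, and the effect on precision is at most about 2 percentage points of half-width under the approximation used. The conclusion is confined to internal consistency. It does not extend to a miscalculated sample size or a compromised Intent-to-Treat analysis.

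**What to change.** State one randomized ceiling in the protocol synopsis, protocol 12.1 and SAP 3.2. The sponsor must say which figure is intended.

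- If it is 50: up to 50 women randomized 1-1-1 (16–17 per arm), with about 45 (15 per arm) expected in the efficacy analysis.
- If it is 45: 45 randomized (15 per arm) throughout, with the number expected for efficacy analysis restated, since 45 can no longer be assumed to allow for any loss.

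In either case, add that the efficacy analysis includes every woman randomized and dosed. The eligibility wording then stands as a planning expectation and cannot be read as a condition for inclusion. It would help to add a few words on why about five women are expected to be lost, because the Intent-to-Treat definition removes only those never dosed.

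The cost is a wording change in three places, with no extra patients and no change of method.

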12.2 Statistical and Analytical Plan

A Statistical Analysis Plan (SAP) will be prepared prior to unblinding the data. The first efficacy analysis will be conducted when all subjects complete the first cycle of treatment. A second analysis will summarize the subject's additional treatment cycles which will be conducted after all subjects complete study treatment and follow-up in Stage 2. In this Phase 2 study there will be no statistical corrections for interim analyses or multiple comparisons.

For the statistical analysis at the end of the first course of treatment, only statistical staff will be unblinded. All clinical operations staff and staff at investigative sites will remain blinded until completion of the study.

12.2.1 Demographics and Subject Characteristics

For all subjects included in this study, subject accountability, baseline demographic and medical history data will be summarized for each treatment group. Summaries for quantitative variables include the sample size, mean, median, standard deviation, minimum, and maximum. Summaries for categorical variables include the number and percent of patients for each outcome. No statistical testing will be performed to compare these factors between treatment groups.

12.2.2 Efficacy Analyses

A Statistical Analysis Plan (SAP) will be prepared prior to unblinding of the study data. Efficacy analyses will be conducted in the Intent-to-Treat population, which will consist of all subjects who are randomized and who receive study drug.

12.2.2.1 Primary Endpoint: Incidence of Amenorrhea

The percentage of subjects who become amenorrheic during the 28 days leading up to the last day of dosing at Week 18 will be compared by Chi-Square test. Amenorrhea after a second course of treatment will be analyzed as a secondary endpoint. Testing will evaluate the pooled Proellex doses compared to placebo, each Proellex dose compared to Placebo as well as compare the active dose groups. A Fisher's Exact test will be utilized if the cell sizes are small.

A subject is deemed amenorrheic if they have no bleeding intensity score greater than 1 using the Daily Diary Card in [Appendix 3](#) (spotting not requiring hygiene products) during the 28 day period.

12.2.2.2 Secondary Endpoints

Percentage Change in PBAC scores

The percentage change in PBAC scores over each 28 day period for each menstrual cycle will be recorded and compared to baseline to determine onset of benefit. Additionally PBAC scores will be used to monitor the level of vaginal bleeding during the ODI and the time to return to baseline vaginal bleeding to determine duration of benefit during the five menstrual cycle follow-up after dosing Course 2.

Within treatment group paired t-tests will evaluate treatment effect. Pairwise comparisons of the treatment groups will be made using a two-sample t-test as well as compare the pooled Proellex doses to placebo. While the primary assessment will be after 18 weeks of treatment, summaries will be prepared for each of the other visits. If data are missing, a last observation carried forward procedure will be used, including the baseline, if necessary. Non-parametric methods will be employed as appropriate.

Percentage change in total and individual symptom severity scores for the UFS-SSS

The UFS-SSS is an 8 question symptom severity score and has been validated as a three month look back questionnaire. The survey will be administered at the baseline of each dosing course and at the end of each course. An analysis of UFS-SSS scores will compare the pooled Proellex dose results to the placebo group with a t-test. Pairwise comparisons of the treatment groups will be made using a two-sample t-test. Within group paired tests will also be used to assess treatment effect. Non-parametric methods will be employed as appropriate. The primary assessment will be based on Visit 12 (after 18 weeks of treatment). If data are missing, a last observation carried forward procedure will be used, including the baseline, if necessary.

Percentage Change in Uterine Fibroid Volume by MRI

The percent change from baseline in total uterine fibroid volume will be determined at the end of each 18 week dosing course and after the 6 months of recovery menses (Visit 24). This study will assess up to 3 fibroids present at baseline in each subject. The volume of these 3 fibroids will be summed to determine the total uterine fibroid volume at each assessment.

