8.1.2 Secondary Endpoints

- Percentage of subjects who become amenorrheic after 2 courses of treatment
- Change and percentage change in PBAC score over the course of the study. Specifically comparing the baseline menstrual cycle to the matching end-of-study period leading up to Week 18 and the end of treatment as well as comparing the baseline PBAC to the ODI time periods.
- Percentage change in UFSQOL Symptom Severity score (UFS-SSS) comparing Week 18 to Baseline (three month look back) and for the ODI.
- Percentage change in the individual UFS-SSS subscores
- Percentage change from baseline in total uterine fibroid volume measured by MRI

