## **5. ENDPOINTS**

Efficacy endpoints will be:

- Percentage of subjects who become amenorrheic
  - Percentage change in PBAC scores
  - Percentage change in total and individual UFS-SSS scores
  - Percentage change in size of uterine fibroids as assessed by MRI
  - Percentage change in uterine volume as assessed by MRI
- 

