### 6.8.3 UFS-SSS

The individual and combined symptom severity scores and percentage change from baseline will be summarized at the end of course 1 treatment, course 2 treatment, and each follow-up visit. Pairwise comparisons between treatment groups will be performed using t-tests and Wilcoxon rank-sum tests, as appropriate. Statistical significance of the change from baseline within treatment groups will be determined using a paired t-test or Wilcoxon signed-rank test, as appropriate.

[figure not shown]

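### Percentage change for single UFS-SSS questions has no low-baseline rule, so an arm's mean can carry the wrong sign or some women can have no value

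*Protocol*

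**What the plan says.** Protocol 8.1.2 lists two UFS-SSS secondary endpoints: percentage change in the overall severity score, and "Percentage change in the individual UFS-SSS subscores". For PBAC the same list asks for both change and percentage change; for UFS-SSS it asks for percentage change only. Protocol 12.2.2.2 treats both endpoints under "Percentage change in total and individual symptom severity scores for the UFS-SSS" and describes the instrument: "The UFS-SSS is an 8 question symptom severity score and has been validated as a three month look back questionnaire".

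The protocol's testing plan is "An analysis of UFS-SSS scores will compare the pooled Proellex dose results to the placebo group with a t-test", followed by pairwise two-sample t-tests and within-group paired tests, with the proviso "Non-parametric methods will be employed as appropriate".

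SAP section 5 names the endpoint as "Percentage change in total and individual UFS-SSS scores". SAP 6.8.3 is broader: "The individual and combined symptom severity scores and percentage change from baseline will be summarized at the end of course 1 treatment", and again after course 2 and at follow-up visits. Raw scores are therefore summarised as well. Its within-group test is worded "Statistical significance of the change from baseline within treatment groups will be determined using a paired t-test or Wilcoxon signed-rank test, as appropriate". The between-group tests are t-tests or Wilcoxon rank-sum tests, and the section does not say whether they use scores, change in points or percentage change.

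SAP 6.1 requires the median beside the mean, and rank-based tests if Shapiro-Wilk shows that normality fails. The SAP version written for Amendment 3 reads the same in these sections.

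The available text states no item coding, no rule for a zero or minimum baseline, and no minimum symptom score for entry. Some entry criteria are redacted, so the last point covers visible text only.

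**The concern.** A single question is a short ordinal score with an arbitrary starting value, and percentage change divides by it. A woman who barely has a symptom at baseline then gets either no value or a very large weight if she worsens, while a woman with a severe symptom who improves by one step gets a small weight. In arms of 15, one or two women can set the sign of the mean.

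What is at stake is how item-level secondary results read. The reported mean percentage could contradict the raw scores, the median and the p-value beside it. Women without a symptom at entry could also disappear from that item's result. The imputation rules in Protocol 12.3 and SAP 6.1 deal with missing observations and do not cover a zero denominator.

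**Working it through.** The plan gives no expected value, SD or power for UFS-SSS, so there is no figure of its own to reproduce. The check is direct arithmetic.

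**Inputs.** From the documents: 15 per arm (Protocol 12.1), 8 questions (Protocol 12.2.2.2), two-sided 0.05 (SAP 6.1). Assumed: individual scores are the single questions, coded either 0-4 or 1-5.

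**Formula.** Per woman, 100 x (follow-up - baseline) / baseline, then averaged over the arm.

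**Coded 0-4.** A baseline of 0 gives division by zero. If 10-20% of women sit at the floor on an item (an assumption), 0.10 x 15 = 1.5 to 0.20 x 15 = 3 women per arm have no value.

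**Coded 1-5.** The limits are 100 x (1 - 5)/5 = -80% and 100 x (5 - 1)/1 = +400%. Every value is defined, but the range is lopsided.

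| Arm of 15 | Mean change, points | Mean % change | Median % |
|---|---|---|---|
| 14 go 5 to 4, one 1 to 4 | (-14 + 3)/15 = -0.73 | (-280 + 300)/15 = +1.3 | -20 |
| 14 go 5 to 4, one 1 to 5 | (-14 + 4)/15 = -0.67 | (-280 + 400)/15 = +8.0 | -20 |
| 13 go 5 to 4, two 1 to 3 | (-13 + 4)/15 = -0.60 | (-260 + 400)/15 = +9.3 | -20 |
| 12 go 5 to 4, three 1 to 2 | (-12 + 3)/15 = -0.60 | (-240 + 300)/15 = +4.0 | -20 |
| 14 go 5 to 3, one 1 to 5 | (-28 + 4)/15 = -1.60 | (-560 + 400)/15 = -10.7 | -40 |

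The last row marks the limit: with two-step gains, one woman is not enough to reverse the mean. In the 5-to-4 against 1-to-4 pattern with k women worse, the mean percentage is positive when 300k > 20(15 - k), so from k = 1. The mean in points is positive when 3k > 15 - k, so from k = 4.

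**How often.** This was an illustrative simulation of an arm of 15 on a 1-5 item, with steps of -2, -1, 0, +1, +2 at probabilities 0.15, 0.35, 0.30, 0.15, 0.05, clipped to the scale. The mean change in points was an improvement while the mean percentage was positive in about 6% of arms with mostly high baselines, 17% with even baselines and 20% with mostly low baselines. In simulated arms with no true effect, the two means had opposite signs in about 9-16%.

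**What the SAP's safeguards do.** In the first row, Shapiro-Wilk on the percentages gives p of about 1e-7, so the SAP moves to the signed-rank test. That gives p = 0.005 for improvement, where the t-test on percentages would give p = 0.95. For 13 against 2 the signed-rank p is 0.057, and for 12 against 3 it is 0.28. None of these shows significant worsening.

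**Power.** This was simulated for a 1-5 item, 15 v 15, latent shift 1.0, within-woman SD 1.0 and four assumed baseline distributions.

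| Method | % change v points |
|---|---|
| t-test only | 60 v 64, 51 v 56, 59 v 62, 47 v 51 |
| With Shapiro-Wilk switch | 61.0 v 62.0, 52.4 v 53.0, 59.2 v 59.1, 48.3 v 48.4 |

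Normality was rejected in at least one arm in 78-98% of runs. Under the SAP's method the gap is at most 1 percentage point.

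**Total score.** A 10-point fall from 28 to 18 on an 8-40 scale is -10/28 = -35.7%. The same fall on that scale started at zero is 20 to 10, or -50%. The percentage depends on the origin; the change in points does not.

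**The case against.** The strongest reply is that the SAP already deals with the worked example. The median of -20% stands beside the mean of +1.3%, the raw scores are summarised, and the rank test points to improvement. SAP 6.8.3 words the within-group test as change from baseline, without the word percentage. The reversal needs small gains among improvers and worsening from the floor. These are secondary endpoints in a small Phase 2 study, and percentage change in a total score is a common convention.

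Most of this stands. A reader might infer three stronger things that the documents do not support:

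- That an item improving in nearly every woman would be concluded to have worsened. Only the mean percentage reverses.
- That power is lost. The loss of a few points seen with t-tests nearly vanishes under the SAP's switch to rank tests.
- That values will be undefined. That depends on zero-based coding, and the questionnaire is not in the available text.

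What the reply leaves open is narrower. A rank test cannot rank a value that does not exist. The mean percentage is still a planned summary and can contradict the results next to it. The between-group tests do not name their scale, while section 5 names percentage change as the endpoint.

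**Conclusion.** The point holds in a limited form. For single UFS-SSS questions, percentage change is either undefined at the floor (0-4 coding) or lopsided from -80% to +400% (1-5 coding), and no low-baseline rule is visible. On 1-5 coding, the worked arms show one to three women of 15 who worsen from the floor making the mean percentage positive while 12 to 14 improve and the mean change in points is negative. How often this would happen depends on the baseline distribution: about 6-20% of arms in the illustrative simulation. The effect is confined to the reported mean percentage and to any undefined values.

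For the total, preferring points is mostly convention; the definite gaps are that the percentage depends on the scale's origin and that the tested scale is not named. The conclusion rests on reading individual scores as single questions and on the two assumed codings. The primary amenorrhea analysis is not touched. The change is worth making because it is simple and nearly free.

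**What to change.** In Protocol 8.1.2 and 12.2.2.2 and SAP 5 and 6.8.3:

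- For each individual UFS-SSS item, make absolute change from baseline in points the measure that is both analysed and tested. Report the between-arm difference with a 95% CI, and drop percentage change for single items.
- For the total, report absolute change in points beside the percentage change, and state which of the two the between-group and within-group tests use.
- State the item coding and the origin of the total. Say how a zero baseline total is handled if the scale allows one.

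The cost is wording in the two documents. The data, visits and families of tests stay the same. The one small downside is that item results can be compared less directly with any earlier report given in percentages.
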